### **4.1. General Definitions**

**Age:** Will be calculated as the integer part of the difference between birth date and the date of informed consent divided by 365.25. Birth date with missing day will be imputed as day 15 and birth data with missing day and month will be imputed as 30-June.

**Adverse Event:** any newly occurring event or previous condition that has increased in severity or frequency since administration of the first dose of study drug.

### **4.2. Sample Size**

There is no formal sample size calculation for this study. Although the sample size is not based on statistical power considerations, administration of TPOXX 600 mg to 300 subjects provides approximately 95% probability of observing at least 1 occurrence of any AE if the incidence of AEs in the study population is 1% and is considered adequate to provide a reasonable assessment of safety and tolerability. A sufficient number of subjects will be randomly assigned to ensure that at least 300 subjects receive at least 92% of the doses of the BID or TID dosing regimen of oral TPOXX 600 mg over the 28-day treatment period.

### **4.3. Randomization, Stratification, and Blinding**

Healthy subjects will be randomized to receive:

- Treatment Group 1: An oral dose of 600 mg ( $3 \times 200$ -mg capsules) TPOXX BID (every 12 hours [ $\pm 30$  minutes]) for subjects with a body weight of 120 kg or less or TID (every 8 hours [ $\pm 30$  minutes]) for subjects with a body weight more than 120 kg for 28 days (Day 1 to Day 28).
- Treatment Group 2: An oral dose of placebo (3 capsules identical to TPOXX) BID (every 12 hours [ $\pm 30$  minutes]) for subjects with a body weight of 120 kg or less or TID (every 8 hours [ $\pm 30$  minutes]) for subjects with a body weight more than 120 kg for 28 days (Day 1 to Day 28).

Randomization will occur according to the randomization schedule and will happen before the study drug administration on Day 1 after informed consent has been obtained and after it has been confirmed that the subject fulfills all eligibility criteria. Subjects will be randomly assigned to 1 of 2 treatment groups using a 4:1 ratio so that 4 subjects will receive TPOXX and 1 subject will receive placebo. This will be based on a randomization schedule prepared by a PPD biostatistician before the study. The groups will be stratified by age groups (18 to 30 years, 31 to 45 years, 46 to 64 years, and 65 to 80 years).

This study will employ a double-blind study design. Treatment assignment will not be known to the subjects, the Sponsor, the investigator, or the staff who are involved in the clinical evaluation of the subjects and the analysis of data. The randomization schedule will be generated by an unblinded randomization statistician at PPD according to PPD's standard operating procedures.

The medical monitor will be responsible for maintaining the blind throughout the study. If a subject becomes seriously ill or pregnant during the study, the blind will be broken only if knowledge of the administered study drug will affect that subject's available treatment options. In the event of a medical emergency requiring identification of the study drug administered to an individual subject, the investigator will make every attempt to contact the medical monitor to explain the need for opening the code within 24 hours of unblinding the subject's randomization assignment. The investigator will be responsible for documenting the time, date, reason for the code break, and the names of the personnel involved. All unblinding activities will be tracked via an audit trail in IWRS. Requests for unblinding of a subject's randomization assignment will be made through the IWRS after consultation with the medical monitor. Subject code breaks by the investigator will result in withdrawal of the subject from the study. The date, time, and reason for the unblinding must be documented on the appropriate page in the eCRF, and SIGA must be informed as soon as possible. The treatment assignment of subjects will remain blinded until all clinical evaluations have been completed. Unblinding at the end of the study will occur only by written request from the lead statistician to the unblinded randomization statistician and the unblinded IWRS team after database lock and confirmation of protocol deviations. The DSMB may request to unblind the treatment assignment of a subject or the study at any time.

#### **4.4. Administration of Study Medication**

Study Medication will be provided to subjects in 4 or 6 bottles (depending on weight which determines BID or TID daily dosing regimen), which is equivalent to 56 or 84 doses. Subjects will be randomly assigned to receive 4 or 6 bottles each containing 42 capsules of 200 mg TPOXX capsules or matching placebo. Each daily dose will be 3 capsules taken orally twice or three times a day for a total of 6 or 9 capsules per day depending upon subject weight.

## **4.5. Endpoints**

### **4.5.1 Safety Endpoints**

The primary outcome measure is the evaluation of the safety and tolerability of twice or three times daily oral dosing of TPOXX 600 mg for 28 days through adverse event (AE) findings, clinical laboratory tests, vital sign measurements, electrocardiogram (ECG) tests, and physical examinations. The primary endpoint is the AE rate. Other endpoints include severe AE rate, time to first AE and time to withdrawal for any reason.

### **4.5.2 Pharmacokinetic Endpoints**

The plasma samples will be collected at specific time points before and after dosing to evaluate the appropriate pharmacokinetic (PK) endpoints for TPOXX after treatment with oral TPOXX 600 mg twice daily or three times daily in the PK subset. A validated bioanalytical method will be used to analyze plasma samples for quantification of TPOXX. For relevant PK timepoints, please refer to [Section 8.2](#).

## **4.6. Analysis Sets**

All populations will be identified and finalized before the database lock. All subjects who are randomly assigned are considered study subjects.

### **4.6.1 Intent to Treat (ITT) Population**

The Intent-to-Treat (ITT) Population will include all subjects who were randomly assigned to the study (i.e., a randomization number and randomization date are present in the database).

This population will be used for summaries of subject disposition.

### **4.6.2 Safety Population**

The Safety Population is defined as all subjects who received at least 1 dose of study drug (TPOXX or matching placebo).

The Safety Population will be used for all summary and analysis of safety endpoints.

### **4.6.3 Per-Protocol Safety Population**

The Per-Protocol (PP) Safety Population will include all subjects who received at least 92% of the 600 mg BID or TID dosing regimen of TPOXX or matching placebo.

If a subject takes less than 92% of study drug, then they will be considered ‘Course Too Short’ but will be included in the safety analysis.

The Per-Protocol Safety Population will also be used for all summary and analyses of safety endpoints.

#### **4.6.4 Pharmacokinetic (PK) Population**

The PK Population will include all subjects in the Per-Protocol Safety Population who have taken at least 2 doses of study drug in sequence, have sufficient TPOXX plasma concentrations, and who have no protocol deviations or other circumstances that would exclude the subject from analysis.

Potential subject exclusions will be determined on a case-by-case basis before unblinding. For example, where subjects experience issues, which may affect exposure to study drug (e.g., emesis, dosing errors, etc.), data will be reviewed by the study pharmacokineticist and evaluated for exclusion from the PK population on a case-by-case basis. All subjects excluded from the PK population will be documented in the data listings.

All plasma drug concentrations by time profiles will be reviewed by the pharmacokineticist.

The PK Population will be used for the preparation of PK summaries and analysis.

### **5. Subject Disposition**

#### **5.1. Disposition**

A disposition table will be provided by treatment for the number and percentage of subjects enrolled/randomized, completed, and discontinued together with the reasons for discontinuation. This table will also include the number and percentage of subjects recruited into each age group (randomization strata) and the number and percentage of subjects included in each analysis population will also be presented.

Informed consent, eligibility, and randomization details and protocol details will be listed for all enrolled subjects.

The following will be summarized for the overall population and by treatment for all subjects.

- The number of subjects who were enrolled
- The number of subjects who were randomized
- The number of subjects who received each treatment
- The number of subjects who completed the study treatment
- The number of subjects who did not complete the study treatment
- The number of subjects who completed the study
- The number of subjects who did not complete the study (both overall and according to reasons for discontinuation from the study)
- The number of subjects in each analysis population

Subject disposition will be summarized by dose level and overall based on ITT population using frequency distribution or descriptive statistics. Subjects who complete, withdraw consent, or are terminated early from the study and the associated reasons will be summarized using frequency distribution.

Baseline demographic and background variables will be summarized by treatment for the ITT, Safety, PP Safety, and PK Populations. The demographics table will also be summarized overall

and by age group as per the stratification used in randomization. For treatment-related tables and listings, the data will be summarized by BID or TID study drug dosing regimen.

## **5.2. Protocol Deviations**

Protocol deviations will be collected during monitoring visits. All protocol deviations are to be recorded in the Clinical Trial Management System (CTMS) with the indication of whether these are major. These data will be listed including the assignment of minor or major. Major deviations are defined as those that may have an impact on subject safety or the validity of the study data (this should be noted in the Clinical Monitoring Plan). The assignment is finalized prior to unblinding.

Major protocol deviations will be summarized overall. All protocol deviations will be presented in a data listing, including the categorization of the deviation as major or minor.

## **5.3. Inclusion and Exclusion Criteria**

All inclusion/exclusion criteria deviations recorded in the electronic case report form (eCRF) will be presented in a data listing.

# **6. Demographics and Other Baseline Characteristics**

## **6.1. Demographics**

The descriptive summaries of demographic and baseline characteristics will be presented for the Safety, PP Safety and PK Populations. The demographics table will also be summarized overall and by age category as per the stratification used in randomization.

For all ITT subjects, demographic data to be summarized include: age (years), gender, race, height (cm), and weight (kg) at screening, and ethnicity. A subject's age in years is calculated using the date of the informed consent and date of birth. Age (years) and baseline weight (kg) will be summarized using descriptive statistics. The number and percentage of subjects by race (American Indian or Alaska Native, Asian, Black or African American, Native Hawaiian or Other Pacific Islander, and White), ethnicity (Hispanic or Latino, Not Hispanic or Latino). Percentages will be based on the total number of subjects in the Safety Population.

Subject demographic and baseline characteristics will be presented in a data listing.

## **6.2. Medical History**

Previous and concurrent diseases/conditions will be listed for all ITT subjects sorted by treatment group, subject, and start date. A complete medical history will be obtained, including recreational, prescription drug use, over-the-counter drug use, nicotine and alcohol use, and past hospitalizations.

Medical history will be coded using the Medical Dictionary for Regulatory Activities (MedDRA, version to be delineated in the clinical study report [CSR]).

Medical history will be presented in a data listing.

## 7. Treatments and Medications

### 7.1. Prior and Concomitant Medications

Medications taken are to be recorded for each subject from screening through day 42 or Day 58 for subjects with any SAEs. Medications that stop within 30 days of the first dose of study drug will be classified as prior medication. Medications that start on or after the first dose of study drug will be classified as concomitant. If a medication starts before the first dose of study drug and stops on or after the first dose of study drug, then the medication will be classified as both prior and concomitant.

Concomitant medications taken by subjects will be recorded at each study visit up to the follow-up telephone call on Day 42. Concomitant medications related to SAEs will be collected and recorded at the Day 58 follow-up telephone call. Subjects will be instructed to record concomitant medications in the subject diary. Any concomitant medication deemed necessary for the welfare of the subject during the study may be given at the discretion of the investigator. If a concomitant medication that meets exclusion criteria is taken during the study, it will be documented as a protocol deviation and a joint decision will be made by the investigator and SIGA to continue or discontinue the subject based on the time the medication was administered, its pharmacology and PK, and whether the use of the medication will compromise the safety of the subject or the interpretation of the data.

All medications will be listed for all safety subjects by treatment group and dosing regimen, subject and start date, and those taken between Day 1 post-dose through to Day 28, i.e., concomitant will be indicated. See SAP [Section 4.0](#) which describes how to deal with partial dates when determining whether a medication is concomitant or prior. Any prior medication will be flagged in the listings. Prohibited medication are indicated in section 4.2 of the protocol. Any subject taking a prohibited medication will be considered a protocol deviator. Prohibited medications will also be flagged in the data listing.

Prior and concomitant medications will be summarized overall for all subjects by treatment.

Prior and concomitant medications and therapies will be coded using the latest version of the World Health Organization Drug Dictionary.

All prior and concomitant medications will be presented in a data listing.

### 7.2. Medical or Surgical Treatment Procedures

Medical or surgical treatment procedures will be presented in a data listing.

### 7.3. Study Treatment

The investigational drug administration and drug accountability data will be summarized by treatment and treatment regimen and presented in the data listings. Visit name, study treatment, date and time of administration, route of administration, actual dose, amount of drug dispensed and adjusted, as well as reason for adjustment, and TPOXX concentration will be recorded.

#### **7.4. Meals**

Subjects will receive a subject diary where they'll keep track of meal consumption. Meal data, which includes time of meal and whether or not the required meal was eaten will be summarized by treatment arm.

Meal data will be presented in a data listing.

### **8. Analysis of Pharmacokinetics**

The ITT Population will be used for the presentation of subjects in all subject listings. The PK population will be used for the pharmacokinetic analysis. Pharmacokinetic tables, mean figures, and all statistical analyses will be presented using data from the PK population.

#### **8.1. Collection Schedule**

Serial blood samples will be collected at the following time points for PK assessment:

- BID Dosing (Subjects weighing 120 kg or less)
  - Day 1: Before the first dose (0 hour) and at 2, 4, 6, 8, 10, 12 (before the second dose), 14, 16, 18, 20, 22, and 24 hours (before the first dose on Day 2)
  - Day 14: Before the first dose (0 hour)
  - Day 28: Before the first dose (0 hour) and at 2, 4, 6, 8, 10, 12 (before the second dose on Day 28), 14, 16, 18, 20, 22, 24 (Day 29, AM), 48 (Day 30, AM), and 72 (Day 31, AM) hours after the first dose on Day 28
- TID Dosing (Subjects weighing more than 120 kg)
  - Day 1: Before the first dose (0 hour) and at 2, 4, 6, 8 (before the second dose), 10, 12, 14, 16 (before the third dose), 18, 20, 22, and 24 hours (before the first dose on Day 2)
  - Day 14: Before the first dose (0 hour)
  - Day 28: Before the first dose (0 hour) and at 2, 4, 6, 8 (before the second dose), 10, 12, 14, 16 (before the third dose), 18, 20, 22, 24 (Day 29, AM), 48 (Day 30, AM), and 72 (Day 31, AM) hours after the first dose on Day 28

For PK blood samples, the acceptable window for collection from the scheduled collection time point will be as follows:  $\pm 15$  minutes from 0 to 24 hours (except where samples are collected predose) and  $\pm 60$  minutes from 48 to 72 hours.

Individual plasma concentrations and time deviation data will be presented in data listings.

Plasma concentration data will be summarized using descriptive statistics (number of observations, arithmetic mean, SD, CV, median, minimum, and maximum) by study day, time point, and study drug dosing regimen.

Individual plasma concentrations versus nominal time will be plotted on both linear and semi-logarithmic scales. Mean plasma concentrations versus scheduled time will be plotted by study day and study drug dosing regimen on both linear and semi-logarithmic scales.

## 8.2. Data Handling

Data rounding specifications for PK data are documented in the PK table, listing, and figure shells.

Plasma concentrations that are below the limit of quantification (BLQ) will be replaced by zero for calculation of concentration descriptive statistics. Mean BLQ concentrations will be presented as BLQ, and the SD and coefficient of variation (CV) will be reported as not applicable. Missing concentrations will be excluded from the calculations.

Non-compartmental PK parameters for TPOXX will be calculated. Actual sampling times will be used in the determination of the individual PK parameters.

### Handling of Dropouts or Missing Data

Missing concentration data for all subjects who take scheduled study drug treatment will be considered as non-informative missing and will not be imputed.

The following rules will apply for the derivation of all kinds of AUCs:

- Concentration values that are BLQ for pre-dose samples will be treated as zero.
- The sampling time relative to dosing for pre-dose samples will also be treated as zero.
- Concentration values that are BLQ before the first quantifiable concentration will be treated as zero.
- Post-dose BLQ values after the first quantifiable time point that are flanked or followed by measurable concentrations will be set to half the value of BLQ.
- Post-dose BLQ value after first quantifiable time point that are not followed by measurable concentrations will be replaced by zero.

If the actual time of sampling is missing, the nominal time may be used.

No further imputation will be applied to any missing values.

## 8.3. Plasma Pharmacokinetic Parameters and Definitions

Plasma concentration-time data will be analyzed by non-compartmental analysis using Phoenix® WinNonlin® Version 8.0 or higher (Certara USA, Inc., Princeton, NJ). The following PK parameters will be calculated for TPOXX, where data permit:

$C_{\max}$	Maximum observed drug concentration in plasma, reported separately for each dose.
$C_{\text{avg}}$	Average steady-state drug concentration in plasma, calculated as: $AUC_{\text{tau}} / \tau$ (Day 28 only)
$C_{\text{trough}}$	Trough plasma concentration (Day 28 only).
$C_{\min}$	Minimum observed drug concentration in plasma (Day 28 only).
$T_{\max}$	Time of maximum observed drug concentration in plasma.
$AUC_{0-24}$	Area under the plasma concentration-time curve (AUC) from time 0 to 24 hours, calculated using the linear trapezoidal rule.

$AUC_{\tau}$	AUC from time zero to $\tau$ where $\tau$ is the 8-hour or 12-hour dosing interval following the first dose, calculated using the linear trapezoidal rule
$AUC_{(0-\text{last})}$	AUC from time 0 to the last measurable observed concentration ( $C_t$ ), calculated using the linear trapezoidal rule (Day 28 only).
$\lambda_z$	Observed elimination rate constant, where $\lambda_z$ is the magnitude of the slope of the linear regression of the log concentration versus time profile during the terminal phase. (Day 28 only).
$t_{1/2}$	Apparent terminal elimination half-life, calculated as: $\ln(2) / \lambda_z$ . (Day 28 only).
$CL_{ss}/F$	Apparent total body clearance, calculated as: Dose / $AUC_{\tau}$ (Day 28 only).
$V_z/F$	Apparent volume of distribution during the terminal phase, calculated as: Dose / [ $\lambda_z * AUC_{\tau}$ ] (Day 28 only).
$RacC_{\max}$	Accumulation ratio based on $C_{\max}$ , calculated as: $C_{\max}$ (following first dose on Day 28) / $C_{\max}$ (following first daily dose on Day 1).
$RacAUC$	Accumulation ratio based on AUC, calculated as: $AUC_{\tau}$ (following first dose on Day 28) / $AUC_{\tau}$ (following first daily dose on Day 1).
Fluctuation	Calculated as: $(C_{\max} - C_{\tau}) / C_{\tau} * 100$ (Day 28 only).

In addition to the above PK parameters, which will be listed and summarized, the following parameters will also be listed to document the selection of data points used to estimate  $t_{1/2}$  using non-compartmental procedures:

Number points	Number of data points used to estimate $\lambda_z$ ; a minimum of 3 data points must be used, and $C_{\max}$ must not be included (Day 28 only).
$\lambda_z$ lower	Lower bound used for the estimation of $\lambda_z$ (Day 28 only).
$\lambda_z$ upper	Upper bound used for the estimation of $\lambda_z$ (Day 28 only).
Span	Number of elapsed half-lives over which $\lambda_z$ is estimated, calculated as $(\lambda_z$ upper – $\lambda_z$ lower) / $t_{1/2}$ . (Day 28 only)
Rsq	$r^2$ , the coefficient of determination (goodness of fit statistic); $\lambda_z$ and all associated parameters will only be reported where $r^2 \geq 0.80$ . (Day 28 only)

Actual sampling times will be used for the estimation of all matrix PK parameters, and all concentrations will be included in the analysis (including concentrations collected outside predefined collection windows).

Plasma PK parameters will be presented in data listings and summarized separately using descriptive statistics (number of observations, arithmetic mean, SD, CV, geometric mean,

geometric SD, geometric CV, median, minimum, and maximum) by study day and study drug dosing regimen.  $T_{max}$  will be summarized using number of observations, median, minimum, and maximum only.

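### SAP 8.3 gives the label Fluctuation to a trough-denominated quantity (percent swing) and leaves Ctau undefined, so the reported value will not be peak-trough fluctuation over the average

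*Combined protocol and SAP*

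**What the plan says.** The protocol lists %Fluctuation among the Day 28 PK parameters, in the synopsis and in Section 6.1. It gives no formula in either place, and its abbreviation list has no entry for the term.

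The SAP supplies the only formula. In the Section 8.3 table the Fluctuation row reads "C_{\max} - C_{\tau}) / C_{\tau} * 100", for Day 28 only. Other rows of the same table bear on it:

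- Cavg: "Average steady-state drug concentration in plasma, calculated as" AUCtau divided by tau, Day 28 only.
- Cmin: "Minimum observed drug concentration in plasma (Day 28 only").
- Ctrough: "Trough plasma concentration (Day 28 only").
- AUCtau: tau "is the 8-hour or 12-hour dosing interval following the first dose, calculated using the linear trapezoidal rule".
- Cmax: reported for each dose separately, with no restriction to one study day.

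Ctau has no row and is not equated to Ctrough or Cmin. Both accumulation ratios name the first Day 28 dose; the Fluctuation row names no dose. PK parameters are summarized "by study day and study drug dosing regimen".

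**The concern.** In ordinary PK usage, fluctuation is the peak-to-trough range relative to the average concentration, and the range relative to the trough is swing. This SAP computes the two inputs that fluctuation needs beyond Cmax, namely Cmin and Cavg, and then uses neither. A reader of the PK parameter summary (Table 14.2.2) would take a number scaled to the trough for one scaled to the average.

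The row is also open to more than one reading. Ctau may mean the listed Ctrough or another end-of-interval sample, and Cmax may follow any of the two or three Day 28 doses. Two programmers could follow the SAP faithfully and report different values.

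What is at stake is the meaning of one parameter under the secondary objective, which is to describe the PK profile.

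**Working it through.** **Inputs from the documents.** The SAP formula; Cavg = AUCtau/tau by the linear trapezoidal rule; tau = 12 h (BID) or 8 h (TID); 2-hourly sampling within the interval ("Day 28: Before the first dose (0 hour) and at 2, 4, 6, 8, 10, 12 (before the second dose on Day 28"). The plan states no numerical fluctuation value, so there is no figure to reproduce.

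**Algebra, no assumptions about kinetics.** Take Ctau as the concentration at the end of the interval (the natural reading).

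- SAP index: S = 100 x (Cmax - Ctau)/Ctau
- Peak-trough fluctuation: F = 100 x (Cmax - Cmin)/Cavg
- Factor: S/F = [(Cmax - Ctau)/(Cmax - Cmin)] x (Cavg/Ctau)

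Over one interval that includes its own end, Cmin cannot exceed Ctau, so the first term is at most 1. The second term exceeds 1 whenever the average is above the end-of-interval value. If Ctau = Cmin, the factor is exactly Cavg/Ctau and S is the larger. If the minimum falls after dosing, because absorption is delayed, the two terms pull in opposite directions. Example: Cmax 2000, Ctau 800, Cmin 500, Cavg 1000 gives S = 100 x 1200/800 = 150% and F = 100 x 1500/1000 = 150%, a factor of 0.8 x 1.25 = 1.

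**Illustration under assumed kinetics.** The documents give no half-life, absorption rate or lag. Assume one compartment at steady state, ka = 0.5 per hour, half-life 8 to 24 h, lag 0 or 2 h. With s the time since absorption of the latest dose began, per unit dose over volume:

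C(s) = [ka/(ka - ke)] x [exp(-ke s)/(1 - exp(-ke tau)) - exp(-ka s)/(1 - exp(-ka tau))], ke = ln 2/half-life.

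Continuous profile:

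| Lag | Half-life | BID: S, F, factor | TID: S, F, factor |
|---|---|---|---|
| 0 h | 8 h | 78.2%, 53.5%, 1.46 | 34.4%, 28.3%, 1.22 |
| 0 h | 24 h | 20.7%, 18.4%, 1.13 | 10.2%, 9.6%, 1.07 |
| 2 h | 8 h | 50.7%, 53.5%, 0.95 | 15.9%, 28.3%, 0.56 |
| 2 h | 24 h | 14.1%, 18.4%, 0.77 | 4.8%, 9.6%, 0.50 |

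**On the SAP's own 2-hour grid** the picture is the same. For BID with an 8 h half-life:

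- No lag: Cmax 1.159, Ctau = Cmin = 0.659, Cavg 0.948. Factor = 0.948/0.659 = 1.44 (S 76.0%, F 52.8%).
- 2 h lag: the same Cmax, Cmin and Cavg, but Ctau 0.779. Factor = (0.380/0.500) x (0.948/0.779) = 0.93 (S 48.9%, F 52.8%).

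TID on the grid at 8 h gives 1.20 with no lag (33.2% against 27.7%) and 0.53 with a 2 h lag (14.8% against 27.7%).

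**Wider assumptions**, on the grid, with half-life 4 to 20 h and ka 0.3 to 1.0 per hour:

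- Lag 0 to 1 h: BID 1.08 to 2.63, TID 1.03 to 1.69.
- Lag 2 h: BID 0.69 to 1.66, TID 0.39 to 0.86.

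**The case against.** The best defence is that the protocol leaves detail to the SAP, the SAP prints an explicit formula, and so the reported value is what the SAP says it is. Cmax, Cmin, Cavg and Ctrough are all listed and summarized, so a reader who wants the other index can rebuild it subject by subject. The convention that separates fluctuation from swing is general PK usage and is not written in these documents. All of that stands, and it keeps the point small. It does not cure a label that does not match its formula, or a Ctau without a definition.

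A reader might infer two stronger claims, and neither is supported.

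- *That the SAP overstates the protocol's %Fluctuation.* The protocol has no formula, so there is no protocol value to overstate. Nor is the direction fixed: the factor is above 1 in the no-lag rows and below 1 in the 2 h lag rows.
- *That the formula distorts the comparison of BID with TID.* With no lag and an 8 h half-life, the BID to TID ratio is 78.2/34.4 = 2.27 on the SAP index against 53.5/28.3 = 1.89 on the other. But no such comparison is planned: parameters are calculated and summarized separately by regimen, and regimen follows body weight, not randomization. The ratio also gives both weight groups the same assumed kinetics. What holds is narrower: the gap between the indices depends on tau, so it differs between the two summary columns.

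**Conclusion.** Wrong as written, minor. The SAP puts the name Fluctuation on percent swing, uses neither Cmin nor Cavg, and leaves both Ctau and the relevant dose unspecified. That follows from the SAP text and the usual meaning of the terms, without any kinetic assumption.

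The size is conditional. With ka 0.5 per hour and half-life 8 to 24 h, all assumed, the SAP value is about 1.07 to 1.46 times peak-trough fluctuation with no lag and about 0.5 to 0.95 times with a 2 h lag. The factor varies by subject and cannot be computed from the documents. Safety analyses, hypothesis tests and sample size are untouched.

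**What to change.** In SAP 8.3, define %Fluctuation = 100 x (Cmax - Cmin)/Cavg, with all three taken from one named Day 28 dosing interval. The interval after the first dose is the obvious candidate, because AUCtau, and hence Cavg, and both accumulation ratios already refer to it. If the present formula is also kept, label it %Swing, define Ctau (stating whether it is the listed Ctrough), and report it beside %Fluctuation. Carry the labels through to Table 14.2.2 and Listings 16.2.6.2 and 16.2.6.3.

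The cost is one table row, or two if both indices are reported. No new sample or data item is needed, since Cmax, Cmin and Cavg are already SAP parameters, and no protocol formula has to change.
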